This Walk with Me study is a two-arm parallel-group randomised trial involving 348 older adults aged 60 years or over living in socio-economically disadvantaged communities. Individuals will be randomised to either a 12-week peer-led walking intervention group or a minimal intervention control group. Baseline measures will be collected before randomisation, at 12 weeks (post-intervention), six months (accelerometer only) and 12 months. An internal pilot will be included with pre-specified stop-go criteria. The independent Trial Steering Committee (TSC) will assess the feasibility of progressing past the first 6-month internal pilot period based on the recruitment rates of peer mentors and participants. Using a 'traffic light' system previously recommended,¹⁹ progression will be based on the percentage of the target sample achieved half way through the recruitment period (6-months): (a) proceed: $\geq 50\%$ of the total sample of peer mentors and participants recruited; (b) modify: 25-49% of the total sample of peer mentors and participants recruited; or stop: $< 25\%$ of the total sample of peer mentors and participants recruited. After six months, any required changes in the recruitment strategy and/or introduction of new recruitment pathways will be agreed with the TSC and the funder. The participants recruited in the pilot study will be included in the overall analysis. Qualitative data will also be collected at 12 weeks and six months. Process and economic evaluations will be nested within the trial.

Setting and Participants

The study will target community-dwelling older adults, aged 60 years or over living in areas of socio-economic disadvantage, defined as most disadvantaged quartile of electoral wards in NI, based on the NI Multiple Deprivation Measure (NIMDM) (www.nisra.gov.uk), which covers a large geographical area.

Recruitment

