In our pilot study, we did not identify clustering of the results by peer mentor, with no obvious pattern in the data. However, as there were relatively few peer mentors involved, this may not be a fair reflection of what might happen in a larger trial. Therefore, based on data from another physical activity study in older adults, we have assumed an ICC of 0.01;²⁸ with a cluster size of 5 participants per mentor, the design effect was estimated as 1.04, resulting in a sample size of 139 per group. Allowing for 20% dropout, a sample size of 174 per group or a total sample size of 348 individuals would be required. This adjustment for clustering thus inflates the estimate derived from the findings of our pilot study.

Walk with Me Intervention

The theoretical design of the Walk with Me intervention is based on social cognitive theory (SCT)²⁹ and the Behaviour Change Wheel is used as an overarching framework.³⁰ Behaviour change techniques (BCTs)³¹ identified from previous evidence were mapped onto the core set of intervention functions of SCT (Figure 2). The socioecological model was used to provide a framework for a multilevel intervention design.³²

Peer mentors and participants will meet once per week in an environment (community centre/coffee shop/library) close to a location where they can also go for a walk together, chosen jointly by the mentor and participant. In choosing a location, any public health or social measures in place due to COVID-19 will be accounted for so that the location is safe to meet

[figure not shown]

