Individuals allocated to the control group will be contacted by a health improvement officer based at the Institute for Public Health. They will be thanked for their participation and informed that they will be contacted at 12 weeks, 6 months and 12 months for follow-up assessments. They will be given a copy of the Public Health Agency's information booklets on active ageing (Appendix 13) and healthy eating (Appendix 14). They will not receive any additional physical activity support over the course of the research study. To encourage retention, they will be contacted again by a health improvement officer at nine months to confirm contact details. Participants in the intervention group will be contacted at the same time to encourage retention. After the final data collection point, they will be given the opportunity to discuss with a member of the research team the availability of local physical activity opportunities (e.g. local walking groups). In line with approaches used in our pilot study¹⁸ and other interventions in older adults,¹³ they will also be offered a pedometer and physical activity diary during this meeting.

Outcome Measures

Demographic and outcome measures will be measured across four time points, as presented in Table 2.

Table 2: Outcome assessment according to the Walk with Me logic model and pilot study.

Data Collection	Baseline	3M	6M	12M
Socio-demographic: age, sex, marital status, car ownership (Appendix 15)	✓			
Actigraph accelerometer	✓	✓	✓	✓
Anthropometry – weight, body mass index (BMI), waist circumference	✓	✓		✓
Resting blood pressure	✓	✓		✓
Short physical performance battery (SPPB) ⁴⁰	✓	✓		✓
Warwick-Edinburgh Mental Well-Being Scale (WEMWBS) ⁴¹⁻⁴² (Appendix 16)	✓	✓		✓
EQ-5D-5L questionnaire ⁴³ (Appendix 17)	✓	✓		✓

UCLA Loneliness Scale ⁴⁴ (Appendix 18) and the Lubben Social Network Scale ⁴⁵ (Appendix 19)	✓	✓		✓
Physical activity self-regulation scale ⁴⁶ (Appendix 20)	✓	✓		✓
Physical activity and social activity self-efficacy ⁴⁷ (Appendix 21)	✓	✓		✓
Physical activity and social activity outcome expectancy ⁴⁸ (Appendix 22)	✓	✓		✓
Service use questionnaire (Appendices 23-25)	✓	✓		✓
Unintended consequences or adverse events		✓		✓

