In the case where COVID-19 public health and social measures make it impossible to meet face-to-face, a pack with outcome measures will be posted to participants in advance of an online video call or telephone call. This will include the accelerometer with instructions on how to fit and wear it, a measuring tape to measure waist circumference and self-completed measures. Participants will be asked to measure their weight using their own scales if they

have them and estimate their height. We will measure as many of the components of SPPB on the video call as is feasible.

Data management and statistical analysis

The primary analysis will be conducted on an intention-to-treat basis once primary outcome data collection is complete, with all randomised patients being analysed in the group to which they were allocated, regardless of the subsequent treatment they received at an a priori significance level of $p=0.05$ and reported in accordance with Consolidated Standards of Reporting Trials guidance.

The analysis will be undertaken by a statistician from the NICTU with no role in decision making about the ongoing conduct of the trial. We will describe baseline characteristics and follow-up measurements using suitable measures of central tendencies; means and medians with the associated standard deviations/interquartile ranges for continuous data; and frequencies and proportions for categorical data.

We will compare the primary outcome between groups adjusting for baseline within a generalized linear mixed model including mentor as a random effect to account for possible clustering. Similar methods will be used for other time-points and secondary outcomes. Exploratory analyses will be reported using 99% confidence intervals using interaction terms (treatment group by subgroup) for the subgroup of high and low household income to look at the moderating effect of individual level socio-economic position. We will also explore the moderating effect of gender, age, season and physical environment features on the results.

Process evaluation

A theory-driven process evaluation will be guided by the MRC Process Evaluation guidelines,⁶⁶ including an understanding of the impact of implementation, mechanisms of impact and context on the study outcomes.

Implementation

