Based on previous research,⁷⁰ these will include the impact of feelings of safety while walking; access to recreational facilities, parks/public open space and shops; greenery and aesthetically pleasing scenery; walk-friendly infrastructure; and access to public transport. To prompt discussion, we will present each focus group participant with a screen shot from the WalkScore (<https://www.walkscore.com>) output for their local neighbourhood. WalkScore is freely available tool that reports walkability within a 30-minute walk from a person's house. The score is a measure of pedestrian friendliness and the number of amenities in the neighbourhood, measured on a scale of 0 to 100. As well as the score, a map is available,

highlighting a variety of local amenities such as parks and shops as well as roads. This will prompt individuals to describe where they walk and what barriers and facilitators to walking they may encounter in their locality.

In addition, we will assess the moderating effect of the physical environment on the results, using WalkScore as a proxy for neighbourhood walkability and area level data on crime and the living environment using relevant indicators from the Northern Ireland Multiple Deprivation Measure (<https://www.nisra.gov.uk/statistics/deprivation/northern-ireland-multiple-deprivation-measure-2017-nimdm2017>).

At 12 weeks and 6 months, we will invite a purposeful sample of 30 intervention group participants to a focus group. A mixture of males and females and different age groups will be invited. We will run between four and six focus groups depending on participants' availability and location. We will also invite their mentors to one of four separate focus groups. They will be provided with a Peer Mentor Participant Information Sheet (v1: 6th November 2021; Appendix 11). Individuals who agree to participate will be asked to provide written consent (v1: 6th November 2021; Appendix 12).

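### The exploratory income-moderation test is fixed as a high/low split; if income is recorded in more than two levels, its recorded scale would use more of the information

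*Protocol*

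**What the plan says.** In Data management and statistical analysis, the Protocol describes the test of moderation by individual socio-economic position as "using interaction terms (treatment group by subgroup) for the subgroup of high and low household income to look at the moderating effect". The same sentence sets the reporting standard: "Exploratory analyses will be reported using 99% confidence intervals".

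Income is not the only moderator named. The next sentence adds others: "We will also explore the moderating effect of gender, age, season and physical environment features on the results". The process evaluation, under Contextual factors, returns to one of them: "we will assess the moderating effect of the physical environment on the results, using WalkScore as a proxy for neighbourhood walkability". It also adds area-level crime and living-environment indicators. Income is, however, the only moderator whose categories are spelled out.

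Three other places bear on the point:
- Setting and Participants restricts recruitment to "areas of socio-economic disadvantage, defined as most disadvantaged quartile of electoral wards in NI".
- Sample Size gives the evaluable number after the clustering adjustment, "resulting in a sample size of 139 per group", but states no power or precision for any interaction.
- Table 2 lists the baseline descriptors as "Socio-demographic: age, sex, marital status, car ownership (Appendix 15"). Household income is not among them, and the appendix itself is not shown.

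**The concern.** A two-level income variable treats everyone on one side of the cut as alike. If benefit rises or falls gradually with income, the variation inside each half is thrown away and the interaction is estimated less precisely than the data allow. Because the Protocol itself fixes the two-level form, an analysis plan that follows it would choose a cut but keep the split.

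Interaction tests in a trial sized for a main effect are weak to begin with, and a 99% interval is wider than a 95% one, so an avoidable loss falls where precision is already poor. At stake is the chance of seeing a real income gradient in benefit in a trial aimed at disadvantaged older adults. Recruiting from one quartile of wards may also narrow the spread of income, so that a high/low line separates people with similar incomes. That is plausible, but the Protocol does not document it.

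**Working it through.** **The plan's own figures.** Sample Size starts from 133 per group for an effect size of 0.4 at 90% power. A two-sided 5% level is assumed, since sidedness is not stated; exact t-test power at 133 is then 0.901. The design effect is 1 + (5 − 1) × 0.01 = 1.04. Then 133 × 1.04 = 138.3, rounded up to 139; 139 / 0.8 = 173.75, rounded up to 174; and 2 × 174 = 348. The plan's figures reproduce. The evaluable total is 2 × 139 = 278. The target of 50 min/week at effect size 0.4 implies an SD of 50 / 0.4 = 125 min/week.

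**Assumptions added here.** The Protocol gives no income scale, distribution, cut or expected interaction. I assume equal arms, a residual SD of 1, moderation linear in the income score, and a two-sided 1% level (critical value 2.576) to match the 99% interval.

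**Step 1: information kept by the split.** Under linear moderation this is the squared correlation between the two-level variable and the original score. For a normal score cut at proportion p, with q the normal quantile at p, it is φ(q)² / [p(1 − p)]. For a uniform score it is 3p(1 − p).

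| Income score and cut | Information lost |
|---|---|
| Normal, median cut (1 − 2/π) | 36% |
| Uniform, median cut | 25% |
| 3, 4, 5 or 6 equal bands, best cut | 25%, 20%, 25%, 23% |
| Cut at one third (uniform to normal) | 33-41% |
| Cut at one quarter (uniform to normal) | 44-46% |
| Raw lognormal income (log-SD 0.5-0.7), median cut | 48-58% |
| True effect is a step at the cut | 0% |

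**Step 2: power.** With income standardised, the SE of the interaction slope is 2/√278 = 0.120, so z = b√278/2 for a slope of b SD of effect per SD of income. A median split of a normal score multiplies z by √(2/π) = 0.798. Power is Φ(z − 2.576), plus a negligible opposite tail.

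| Slope b | In min/week (× 125) | z, full scale | Power, full scale | z, split | Power, split |
|---|---|---|---|---|---|
| 0.1 | 12.5 | 0.83 | 4.1% | 0.67 | 2.9% |
| 0.2 | 25 | 1.67 | 18.2% | 1.33 | 10.7% |
| 0.3 | 37.5 | 2.50 | 47.0% | 2.00 | 28.1% |
| 0.4 | 50 | 3.33 | 77.6% | 2.66 | 53.4% |

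A simulation of 4,000 trials with a steep gradient gave a ratio of squared mean test statistics of 0.61, close to 2/π = 0.64. It falls slightly lower because the gradient left inside each half adds to the residual.

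**Step 3: precision with the split.** For two equal halves the SE of the difference in effect is √(16/278) = 0.240 SD. The 99% half-width is 2.576 × 0.240 = 0.618 SD, or about 77 min/week. Using 266 (2 × 133), the number before the clustering inflation, it is about 79 min/week. Both exceed the 50 min/week the trial is sized to detect.

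**The case against.** The strongest case against has five parts.

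- **The analysis is exploratory.** No power is claimed for it, and no listed objective or research question concerns an income gradient within the sample. This stands and limits the weight of the point.
- **The size of the loss is not a property of the plan.** This also stands. A reader might take 20-36% as what this trial will lose, but it rests on a central cut, a normal or equally banded score and linear moderation. The possible range runs from nothing to more than half.
- **The larger gains need steep gradients.** With an overall effect of 0.4, a slope of 0.4 per SD means no benefit one SD to one side of mean income and double benefit one SD to the other. A narrow income range would make steep slopes per sample SD less likely. At 0.1 to 0.2 the gain is about 1 to 7.5 points, and power stays below 20% either way.
- **The recorded scale is unknown.** If the income item has only two levels, nothing is discarded and the point falls. A reader might infer from Table 2 that income is not collected; with Appendix 15 not shown, the document does not support that.
- **A linear term can also be wrong.** If the truth is a step at the median, a linear normal score loses the same 36%. But a step exactly at the chosen cut is a special case, and the linear form can be checked.

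A reader might also infer that the cut will be chosen after the data are seen. The Protocol gives no cut, but a cut is commonly left to the analysis plan, so its absence is not a fault. The two-level form is different, because the Protocol states it.

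**Conclusion.** The point holds as a low-severity improvement, conditional on income being recorded in more than two levels. The Protocol fixes a high/low income variable without giving a reason, and an interaction using the recorded scale would generally be more precise if benefit changes gradually with income. Under the stated assumptions (278 analysed, normal score, median cut, linear moderation, two-sided 1% level), the power gain is about 1 point at a slope of 0.1, 7.5 at 0.2 and 19 at 0.3.

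Two stronger readings are not supported. Income is not the sole moderator planned, since gender, age, season and physical environment are also named. Nor is the trial's main conclusion at risk: the primary comparison, its 5% level and the total of 348 do not depend on this analysis.

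**What to change.** In Data management and statistical analysis, and provided the income item has more than two levels, replace the high/low subgroup test with a treatment-by-income interaction using income on its recorded scale: ordered bands scored linearly, or log income if amounts are collected. Include the income main effect. Report the interaction slope with its 99% confidence interval, and check linearity by adding a quadratic term or fitting the bands as categories. Keep a high/low table at a prespecified cut for description only.

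The cost is one sentence of analysis wording, with no extra participants or visits. The downsides are a linear-trend assumption, which the check addresses, and a slightly less simple presentation. If the item turns out to have two levels only, no change is needed.

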The primary outcome will be daily minutes of moderate-to-vigorous physical activity per day (>1951CPM) at 12-months,⁴⁹ measured using a waist-worn Actigraph wGT3X+ accelerometer (ActiGraph, LLC, Pensacola, FL, USA) and worn for a minimum of four days out of seven.⁵⁰ To be included in the analysis, standard cleaning rules will be applied (at least five valid days defined as 600 minutes of wear time per calendar day).⁵¹ Non-wear time will be defined as a run of zero counts lasting > 60 minutes.

Secondary outcomes, which were found to be acceptable and feasible in our pilot study, were measures of mental well-being, using the Warwick–Edinburgh Mental Well-being Scale (WEMWBS),⁴¹⁻⁴² and quality of life using the EuroQol-5 Dimensions, five-level version (EQ-5D-5L) questionnaire.⁴³

In our logic model (Appendix 26) we define physical activity and social activity self-efficacy (10-point Likert scale, rating confidence in the ability to remain physically or socially active despite circumstances such as bad weather, boredom and pain),⁴⁷ and physical activity and social activity outcome expectancies (five-point Likert scale rating likelihood of outcomes such as good health, improved appearance, reduced stress, companionship and motivation),⁴⁸ as intermediate outcomes and possible mediators of the intervention, to aid the understanding of the mechanisms through which the intervention works as part of the process evaluation. We will also assess physical activity self-regulation (PASR),⁴⁶ as it indicates the processes through which change is hypothesised to occur. The PASR questionnaire assesses the use of BCTs included in the intervention such as self-monitoring, goal setting and social support. In addition, loneliness and social engagement will be measured with the UCLA Loneliness Scale⁴⁴ and the Lubben Social Network Scale.⁴⁵ As requested by participants in the pilot study, we will also measure resting blood pressure, height, weight, body mass index (BMI) and waist circumference, as these have been shown to be associated with increased physical activity in

older adults.⁵² Physical functioning will also be measured using the short physical performance battery (SPPB).⁴⁰ Light intensity physical activity (>100 & ≤1951 CPM) and sedentary behaviour per day (≤100 CPM) will be calculated from the accelerometer data.

Health economic evaluation

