Dissemination of Findings

We will target programme commissioners, general public and primary care clinicians with targeted outputs, using plain English summaries to ensure all resources are accessible to a wide audience. We will produce a range of outputs for different audiences, including a study website with regular updates, newsletters for participants, stakeholders and policy makers, lay summaries of evidence, peer reviewed publications and conference presentations at national and international conferences. We will prepare papers for publication in the public health literature.

To disseminate the ongoing progress of the study, and the study findings to members of the public and the wider public health community, we will distribute lay summaries of evidence and circulate these via social media channels (Twitter, Facebook). We will also seek three intervention participants to volunteer to keep a regular vlog of their experience of the programme. They will be asked to record a short 30 second video on their mobile phone, describing their experience as they progress through the intervention and to reflect on the process and what they have learnt. These will be collated and shared via Youtube and social media, with the participants' permission (Appendix 33).

Project Timelines

This project will last for 36 months. It is anticipated that all participants will be recruited between April 2022 and March 2023. This will allow for post-intervention assessments to take place between July 2022 and June 2023, 6-month assessments to take place between October 2022 and September 2023, and 12 month assessments between April 2023 and March 2024, leaving nine months for analysis, write-up and dissemination.

References

1. United Nations. World Population Ageing 2017 Highlights. New York: United Nations; 2019.
2. Piercy KL et al. The Physical Activity Guidelines for Americans. *Jama* 2018;320(19):2020-28.
3. Department of Health and Social Care. UK Chief Medical Officers' Physical Activity Guidelines. London: Department of Health and Social Care; 2019.
4. Cunningham C. Consequences of physical inactivity in older adults: A systematic review of reviews and meta-analyses. *Scand J Med Sci Sports*. 2020;30(5):816-827.

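### The baseline-adjusted model is carried to the 12-week and 6-month accelerometer outcomes without a term for time of year, which may cost some precision at those secondary time points

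*Protocol*

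**What the plan says.** Under Data management and statistical analysis, the primary outcome is compared "adjusting for baseline within a generalized linear mixed model including mentor as a random effect to account for possible clustering". The next sentence extends this: "Similar methods will be used for other time-points and secondary outcomes". Season is mentioned once in that section, among the exploratory moderators: "We will also explore the moderating effect of gender, age, season and physical environment features on the results".

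The dates are under Project Timelines:

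- Baseline: "It is anticipated that all participants will be recruited between April 2022 and March 2023".
- 12 weeks: "post-intervention assessments to take place between July 2022 and June 2023".
- 6 months: "6-month assessments to take place between October 2022 and September 2023".
- 12 months: "12 month assessments between April 2023 and March 2024".

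The accelerometer is worn at all four time points (Table 2), and it is the only measure taken at 6 months. The primary outcome is set at the last of them: "The primary outcome will be daily minutes of moderate-to-vigorous physical activity per day (>1951CPM) at 12-months".

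**The concern.** Baseline adjustment deals well with time of year when baseline and follow-up fall in the same season, as they do at 12 months. The protocol carries the same adjustment to visits where they do not. If people walk more in summer than in winter, someone enrolled in summer tends to have a raised baseline and a lowered 6-month value. Seasonal variation then enters the follow-up value, and the baseline becomes a poorer predictor of it.

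What is at stake is the precision of the 12-week and 6-month comparisons of MVPA, and possibly of light activity, sedentary time and steps. These comparisons show whether an effect appears by the end of the 12-week programme and whether it is still there at 6 months, when the mentor calls end.

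**Working it through.** **The plan's own figures.** The sample size reproduces. A two-sided two-group t-test with effect size 0.4 and 90% power needs 132.3, so 133 per group. The design effect is 1 + (5 − 1) × 0.01 = 1.04, and 133 × 1.04 = 138.3, so 139. Then 139 / 0.8 = 173.75, so 174 per group and 348 in total. The implied SD of MVPA is 50 / 0.4 = 125 min/week. None of this depends on season.

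**Inputs that the documents do not give (assumptions).**

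- Peak-to-trough seasonal swing *w*: 0.25 to 0.5 SD, which is 31 to 62 min/week at an SD of 125.
- Correlation *r* between baseline and follow-up apart from season: 0.5 to 0.7.
- Recruitment spread evenly over the year, and a sinusoidal seasonal effect.

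**Model.** Take the non-seasonal variance as 1. The seasonal amplitude is *w*/2, so the seasonal variance is s = (w/2)² / 2. That gives s = 0.0078 for a swing of 0.25 SD and 0.0313 for 0.5 SD. Let φ be the shift in time of year between baseline and follow-up:

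- 12 weeks: φ = 2π × 12/52, cos φ = 0.12
- 6 months: φ = π, cos φ = −1
- 12 months: φ = 2π, cos φ = 1

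Residual variance adjusting for baseline only: V0 = 1 + s − (r + s cos φ)² / (1 + s).

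Residual variance adjusting for baseline and the sine and cosine of the date: V1 = 1 − r².

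**One case in full** (6 months, swing 0.5 SD, r = 0.7). V0 = 1.03125 − (0.66875)² / 1.03125 = 0.5976. V1 = 0.51. The ratio is 0.853, so the date term removes 14.7% of the residual variance. The standard error is multiplied by √0.853 = 0.924.

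**All cases: share of residual variance removed by the date term.**

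| Swing (SD) | r | 12 weeks | 6 months | 12 months |
|---|---|---|---|---|
| 0.25 | 0.5 | 1.2% | 2.3% | 0.3% |
| 0.25 | 0.7 | 2.0% | 4.2% | 0.1% |
| 0.5 | 0.5 | 4.5% | 8.3% | 1.0% |
| 0.5 | 0.7 | 7.4% | 14.7% | 0.5% |

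A simulation of the same model (400,000 draws) agrees to within about 0.001 in the variance ratio. It gave 0.916 and 0.852 at 6 months, and 0.956 and 0.925 at 12 weeks, for a swing of 0.5 SD.

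**In other terms.** At 6 months the standard error falls by about 1% (ratio 0.977) to 8% (ratio 0.853). With 2 × 139 = 278 analysed, that is worth about 278 × (1/0.977 − 1) ≈ 7 to 278 × (1/0.853 − 1) ≈ 48 further participants. In a variant that fixes the total SD at 125, take an amplitude of 20 min/week (a swing of 40/125 = 0.32 SD) and an effect that has 90% power without the date term. Adding the term gives 91.0% to 91.9% power at 6 months, 90.5% to 90.9% at 12 weeks and 90.1% at 12 months.

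**The case against.** The strongest reply is that the protocol gives a short model statement and not a closed list of covariates. Covariates for secondary time points are ordinary SAP content, and the SAP is not shown. This stands so far as it goes: nothing here is a contradiction, a wrong figure or an invalid method, and the SAP may already contain the term. It does not remove the point, because the protocol does state a model and does carry it to visits in another season.

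The size of the gain is assumed throughout. That also stands. The documents contain no data on seasonal activity, and the upper swing of 62 min/week is larger than the 50 min/week difference the trial is powered for. At the lower swing the gain is slight. The calculation is for MVPA only; no separate figure supports a loss for steps, light activity or sedentary time.

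It can also be said that a treatment-by-season model would normally contain a season main effect. That is true, but the protocol makes that analysis exploratory, so it does not change the main 12-week and 6-month estimates.

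Two stronger readings might be inferred, and neither is supported:

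- *The comparisons are biased, or the primary result is at risk.* Individuals are randomised in permuted blocks, so time of year is spread evenly over the arms. The primary measure falls in the same season as its baseline.
- *The season moderator is faulty because season of starting and season of measurement cannot be told apart at 12 months.* With roughly fixed visit intervals, the first largely determines the second at every visit, and no rewording could separate them. The protocol says only that it will explore season and does not claim to separate them.

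**Conclusion.** The point holds as a low-priority suggestion about precision. The stated model is extended to two visits whose season differs from that of baseline, and a covariate that is already recorded could remove the resulting variation. For MVPA the gain is about 2% to 15% of residual variance at 6 months, 1% to 8% at 12 weeks, and 1% or less at the 12-month primary time point. These figures rest on an assumed swing of 0.25 to 0.5 SD, a correlation of 0.5 to 0.7, even recruitment over the year and a sinusoidal pattern. If activity in this population is hardly seasonal, the gain is negligible. The 12-week and 6-month comparisons are valid as planned, and the sample size needs no change.

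**What to change.** In the models for the accelerometer outcomes at 12 weeks and 6 months, pre-specify calendar date of randomisation as a baseline covariate, entered as the sine and cosine of the date over a one-year period. If the SAP already includes such a term, confirming that is enough. The date is fixed before treatment and known for every participant. Because the visit intervals are roughly constant, the two terms account for season at both baseline and follow-up. The cost is one line of model wording and 2 degrees of freedom, with no new data. The 12-month model and the exploratory season analysis can stay as they are.
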